FEASIBILITY STUDY OF ENDOSCOPIC ULTRASOUND-GUIDED FINE-NEEDLE ASPIRATION (EUS-FNA) FOR THE ASSESSMENT OF HYPERMETABOLIC LYMPHADENOPATHIES IN THE LOWER, POSTERIOR AND MIDDLE MEDIASTINUM, DETECTED BY 18FDG PET-CT

APOGEE STUDY SUMMARY

(Apport de la **POnction Guidée sous ÉchoEndoscopie** – Contribution of Endoscopic Ultrasound Guided Aspiration)

Translation of version n°4 of 11/07/2016

Including the substantial modification n°1 of 12/10/2012

Including the substantial modification n°2 of 13/06/2013

Including the substantial modification n°3 of 04/08/2014

Including the substantial modification n°4 of 11/07/2016

**N° IDRCB: 2012-A00985-38 – n° IB: 2012-01
 NCT01892501**

Coordinator

[name] [name]
Medical Oncologist

Department of Medical Oncology

Institut Bergonié

[name]
 [contact] – [contact] – Email: [contact]

Co-Coordinator

[name] [name]
Nuclear Medicine Specialist

Department of Nuclear Medicine

Institut Bergonié

[name]
 [contact] – [contact] – Email: [contact]

Clinical and Epidemiological Research Unit

[name] [name]
Director

Institut Bergonié, Bordeaux

[name] [name]
Epidemiologist

Institut Bergonié, Bordeaux

[name]
Biostatistician

Institut Bergonié, Bordeaux

[name]
Clinical Research Assistant

Institut Bergonié, Bordeaux

Clinical Trials Unit
 [name]
 [name]
Pharmacists

Institut Bergonié, Bordeaux

Pathology Department
 [name] [name]
Pathologist

Institut Bergonié, Bordeaux

PROMOTOR

INSTITUT BERGONIE

SUMMARY

Study title	Feasibility study of endoscopic ultrasound-guided fine-needle aspiration (EUS-FNA) for the assessment of hypermetabolic lymphadenopathies in the lower, posterior and middle mediastinum, detected by 18FDG PET-CT
Promotor	Institut Bergonié
Coordinator	[name] [name] Institut Bergonié
Indication	Mediastinal lymphadenopathies
Methodology	Single center study
Number of patients	50 patients
Study duration	End of inclusions: 31/12/2017 Follow-up duration: 1 year Study duration: 6 years Beginning of the study: 2 nd semester 2012
Objectives Endpoints	
Primary objective: To assess the performance in terms of sensitivity of EUS-FNA for the characterization of mediastinal lymphadenopathies, hypermetabolic on PET, for new cancers or relapse.
 
Secondary objectives:
 
 • Evaluate the negative predictive value of EUS-FNA for the characterization of mediastinal lymphadenopathies, hypermetabolic on PET, for new cancers or relapse. • Evaluate the impact of the combination of the two techniques on diagnostic and therapeutic management. This will be evaluated by: 
 - the percentage of more invasive diagnostic procedures avoided (e.g. surgeries: mediastinoscopy, thoracoscopy) - the possible modification of the therapeutic strategy after endoscopic puncture, compared to the strategy that would have been envisaged after PET alone. • Evaluate the diagnostic performance of this method according to the stage of treatment (diagnosis, evaluation of the therapeutic response or suspicion of relapse), thoracic or extra-thoracic location and the pathological type of the tumor. • Compare tumor characteristics described on PET (size and intensity of lymphadenopathy fixation) in patients with a confirmed diagnosis of cancer and those with a diagnosis of benign pathology (using as reference EUS-FNA when it is positive and the follow-up at 1 year when it is negative), to define more efficient criteria for PET interpretation.
Inclusion criteria	
 1. Patients with a PET showing one or more hypermetabolic lymphadenopathies in the middle and/or lower and/or posterior mediastinum and requiring diagnostic certainty for therapeutic strategy decisions. 2. PET scan performed for the following indications: 
 • Pre-therapeutic assessment of thoracic or extra-thoracic neoplasms (patients without a history of cancer). • Evaluation of the response to cancer treatment. • Suspicion of relapse in patients with a personal history of thoracic or extra-thoracic neoplasms. 3. PET with a positive result: 
 • For lymphadenopathies with a small axis > 1cm: result greater than or equal to the hepatic background. • For lymphadenopathies with a small axis < 1cm: result strictly greater than the hepatic background noise. 4. Patient with an indication for a surgical diagnostic procedure (whether it is feasible or not).

	
 5. Lymphadenopathy(s) accessible to EUS-FNA via the esophagus, that is, allowing a technically feasible aspiration procedure from the esophagus (without recusing vascular structures). 6. Age \geq 18 years old. 7. PET scan performed 6 weeks before endoscopy. 8. Platelets \geq 70,000 / mm³; TP \geq 60%. 9. Patient of childbearing age with negative pregnancy test and / or contraception. 10. Signed informed consent. 11. Patient affiliated to a social security scheme.
Non-inclusion criteria	
 1. General contraindication(s) to performing endoscopy. 2. Unfavorable anesthetic assessment (precluding general anesthesia). 3. Esophageal stenosis. 4. Coagulation disorders. 5. Pregnant or breastfeeding woman. 6. Inability to undergo medical monitoring of the trial for geographic, social or psychological reasons. 7. Adult patient under a legal protection measure or unable to express consent.
Study procedure	
When a patient has a PET scan showing one or more hypermetabolic lymphadenopathies in the lower, middle or posterior mediastinum, his/her file is presented to a multidisciplinary consultation meeting MTM#1, to define the diagnostic strategy: strategy chosen to perform a surgical biopsy to obtain histological documentation of the mediastinal lymphadenopathy with obvious impact on the therapeutic choices.
 
The patient is eligible to participate in the study if the indication for mediastinoscopy is made.
 
The patient is then informed of the study and signs the informed consent if s/he agrees to participate.
 
We differentiate 2 groups of patients depending on the feasibility of the surgical procedure:
 
Group A: surgical biopsy is possible
 
Group B: surgical biopsy cannot be performed (medical or anesthetic contraindications): at that time, definition of the therapeutic strategy that would have been decided in the absence of histological documentation:
 
 • Surgery from the outset • Chemotherapy or other cancer treatment • Non-cancer treatment / patient management for suspected benign pathology • No treatment. 
The EUS-FNA via the esophagus is then performed for the 2 groups of patients (within a maximum of 6 weeks after the PET scan), under general anesthesia and endoscopic control, with a disposable 19-gauge needle (EchoTip, Cook Endoscopy) and with 3 needle passages per node.
 
Pathology samples are taken: 3 tubes taken per lymph node (1 tube per needle passage), in most cases, only 1 lymph node will be taken:
 
 • 2 tubes for oncology analysis • 1 frozen tube for microbiological analysis (mainly tuberculosis) in the event of a negative oncology analysis and if there is evidence of a pathology 
The slides are then read by 2 different pathologists: routine reading by a pathologist from the Institut Bergonié then confirmatory reading by Dr [name].
 
Depending on the pathological results (5 to 6 days delay), the therapeutic

	
pathology, or
 
 if the thoraco-abdomino-pelvic scans carried out at 6 and 12 months after the EUS-FNA indicate the presence of progressive neoplastic pathology. In case of doubt and if the doctor taking care of the patient deems it necessary, additional examinations may be carried out to confirm this diagnosis. 
Absence of malignancy: if the thoraco-abdomino-pelvic scans carried out 6 and 12 months after the EUS-FNA indicate the absence of progressive neoplastic pathology. In case of doubt and if the doctor taking care of the patient deems it necessary, additional examinations may be carried out to confirm this diagnosis.
 
 The technique evaluated is EUS-FNA. In particular, we consider that there is: 
 Diagnosis of malignancy: if the histology carried out on the material taken by the endoscopic puncture shows a malignant tumor. Absence of malignancy: if the histology carried out on the material taken by the endoscopic puncture shows a benign pathology (benign tumor, sarcoidosis). Atypical, suspect or non-contributory result, diagnosis of malignancy / benignity impossible. The sensitivity corresponds to the rate of subjects with a diagnosis of malignancy (without taking into account atypical / suspect or non-contributory results) according to the EUS-FNA results (index test) among all the subjects considered to be suffering from a neoplastic pathology according to the reference test. 
Secondary endpoints are:
 
 The negative predictive value of EUS-FNA will be evaluated. It corresponds to the rate of subjects with a diagnosis of benign pathology according to the reference test among all the subjects for whom EUS-FNA reveals a benign pathology (without taking into account atypical / suspect or non-contributory results). 
Impact on care will be evaluated in 2 ways based on (i) clinical utility and (ii) concordance between the MTM1/ MTM2 therapeutic strategies.
 
The clinical utility of endoscopic ultrasound puncture (Groups A and B)
 
 The puncture will be considered to have clinical utility, if it makes it possible to avoid more invasive diagnostic procedures (mediastinoscopy or thoracoscopy for patients in group A) or if it allows the patient to benefit from an appropriate treatment (result of the malignant biopsy) or to avoid receiving an unjustified treatment (result of the benign biopsy): case of patients well classified in malignant / benign by the EUS-FNA. The EUS-FNA will be considered to have no clinical utility if the result of is invalidated by the reference examination, or if the result of the puncture does not allow a diagnosis to be made. 
Agreement between MTM1 / MTM2 therapeutic strategies
 
In all patients, the agreement between the therapeutic strategies taken before and after the results of the EUS-FNA will be assessed.
 
 Therapeutic strategy for the mediastinal lymph nodes described at inclusion envisaged in MTM 1 
 Surgery from the outset Chemotherapy or other cancer treatment Non-cancer management in the event of a suspected benign pathology No treatment Therapeutic strategy for the mediastinal lymph nodes described at inclusion envisaged in MTM2 
 Surgery from the outset Chemotherapy or other cancer treatment Non-cancer management in case of benign pathology Other surgical diagnostic procedure
--	--

	
 ○ No treatment • Agreement between the 2 strategies considered: for any discrepancy between the 2 strategies considered before the endoscopic puncture and after, the puncture will be considered to have had an impact on the treatment. • Side effects In all cases, the side effects associated with performing the EUS-FNA will be collected and classified according to the Clavien-Dindo classification of surgical complications [Clavien P et al. Ann Surg 2009; 250: 187-96].
Number inclusions necessary of	
This project is an exploratory pilot study, the main objective of which is to evaluate the performance of EUS-FNA via the esophagus, carried out after a PET scan showing hypermetabolic lymphadenopathy. Again, the main judgment criterion is sensitivity.
 
Due to the small amount of data available in the literature concerning the sensitivity and specificity of this examination, we did not calculate a number of patients necessary, but determined the number of patients taking into account the feasibility and recruitment criteria possible at Institut Bergonié as well as acceptable precision of the estimations.
 
For 50 patients, we estimated that the precision of the sensitivity and specificity estimate would be 12% for an expected sensitivity of 95% (95% confidence interval: [89%; 100%]) [Kalade AV et al. Intern Med J. 2008 - sensitivity and specificity of EUS-FNA coupled with PET Scan, but for histology data, whereas in our project we will have cytology data].

Statistical analysis	
Patient characteristics at inclusion
 
The patients included will be described according to the following characteristics:
 
 • Compliance with eligibility criteria • Epidemiological characteristics 
The diagnosed mediastinal lymphadenopathy will be described:
 
 • On PET scan: injected dose, fixation time, location, size of the minor axis (mm), fixation grade (0 to 4), SUV max mediastinal vascular background, SUV max hepatic background, SUV max lymph nodes, SUV max tumor, N / T ratio, N / Liver ratio. • Endoscopic ultrasound: number of lymph nodes, location, shape, size, echogenicity, characteristics of the boundaries. • Quality of samples obtained by EUS-FNA. • Pathological characteristics: malignant tumor, benign tumor or sarcoidosis, atypical or suspect, non-contributory. 
Definitions of the study populations
 
 • Eligible population • All patients meeting the eligibility criteria. Patient eligibility will be established by the steering committee on a case-by-case basis. • Eligible and assessable population for the main criterion 
All the patients included in the study, for whom 1) the eligibility criteria are met, 2) the results of the endoscopic guided puncture are contributory.
 
Analysis of judgment criteria
 
 • The characteristics of the patients at inclusion will be described from the eligible population • The main and secondary criteria will be described on the basis of the eligible and assessable population • Subgroup analyses, in particular by type of cancer, may be

	
considered, but only on an exploratory basis.
 
• Quantitative variables will be described using descriptive statistics (range, quartile and median).• Qualitative variables will be described on the basis of the proportions and presented with their 95% confidence interval.
--	--

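### The treatment-impact rule counts every MTM1/MTM2 change as an effect of the puncture and has no step that asks for the cause

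*Combined protocol and SAP*

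**What the plan says.** The Objectives row sets the target as a contrast between two strategies: "the possible modification of the therapeutic strategy after endoscopic puncture, compared to the strategy that would have been envisaged after PET alone".

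The Evaluation criteria turn this into a before/after comparison: "In all patients, the agreement between the therapeutic strategies taken before and after the results of the EUS-FNA will be assessed". Cause is then assigned by definition: "for any discrepancy between the 2 strategies considered before the endoscopic puncture and after, the puncture will be considered to have had an impact" on treatment. What is compared is limited in scope; the second entry is the "Therapeutic strategy for the mediastinal lymph nodes described at inclusion envisaged in MTM2", and the first is limited in the same way.

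On timing, the Study procedure row places MTM1 after the PET and allows the puncture "within a maximum of 6 weeks after the PET scan". It continues: "Depending on the pathological results (5 to 6 days delay), the therapeutic" strategy is set at MTM2.

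Agreement is not the only impact measure: "Impact on care will be evaluated in 2 ways based on (i) clinical utility and (ii) concordance between the MTM1/ MTM2 therapeutic strategies".

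On the population, the Statistical analysis row says: "The main and secondary criteria will be described on the basis of the eligible and assessable population". That population requires a contributory puncture.

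**The concern.** The objective asks what the puncture adds to PET. The MTM1 entry can stand for the PET-only strategy at the time of MTM2 only if nothing but the EUS-FNA result differs between the two meetings. The plan neither ensures this nor checks it. In a single group with no control, any change with another cause enters the numerator and is reported as an effect of the technique.

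Such changes are plausible. Patients may be in pre-treatment work-up, response assessment or investigation of suspected relapse. For Group B the Study procedure also describes the MTM1 entry as a hypothetical choice, made as if no histology would be available, and a hypothetical choice can shift when the file is discussed again.

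At stake is the interpretation of the strategy-change rate. Under the rule it would be read as the effect of EUS-FNA on treatment, when it measures that effect plus whatever else moved the decision.

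**Working it through.** **The plan's own figure.** The impact endpoint has no expected rate, threshold or sample size, so there is nothing to reproduce for it. The only computed figure is the precision of sensitivity: 1.96 × √(0.95 × 0.05 / 50) = 0.060, a full width of 0.121, in line with the stated 12% and the interval from 89% to 100%. It has no bearing on this endpoint.

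**Timing.** The longest interval from PET to pathology result is 6 × 7 + 6 = 48 days. This is not the MTM1-to-MTM2 interval. MTM1 falls some unstated time after the PET, and MTM2 some unstated time after the pathology result. The gap between the meetings may be several weeks or much shorter.

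**Size, for illustration only.** Let q be the true share of patients whose strategy changes because of EUS-FNA, and b the share who would change for another cause. Neither is in the documents. Assume that the two are independent and that other causes only add discrepancies. Then

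reported rate = q + (1 − q) × b

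| q | b | Reported rate | Excess | Excess in 50 patients |
|---|---|---|---|---|
| 40% | 0% | 40% | 0 points | 0 |
| 40% | 5% | 0.40 + 0.60 × 0.05 = 43% | 3 points | 1.5 |
| 40% | 15% | 0.40 + 0.60 × 0.15 = 49% | 9 points | 4.5 |
| 20% | 0% | 20% | 0 points | 0 |
| 20% | 5% | 0.20 + 0.80 × 0.05 = 24% | 4 points | 2 |
| 20% | 15% | 0.20 + 0.80 × 0.15 = 32% | 12 points | 6 |

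For scale, the 95% half-width with 50 patients is 1.96 × √(0.40 × 0.60 / 50) = 13.6 points at 40%, and 1.96 × √(0.20 × 0.80 / 50) = 11.1 points at 20%.

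**Who is counted.** The Evaluation criteria apply the agreement analysis to all patients; the Statistical analysis row restricts secondary criteria to contributory punctures. The difference matters. A further surgical diagnostic procedure is an option at MTM2 but not at MTM1, and the Study procedure links it to a non-contributory result. If all patients are counted, choosing it is a discrepancy by construction and scores as impact. If only contributory punctures are counted, patients with a non-contributory result drop out.

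**The case against.** The case for leaving the rule alone has real weight.

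- **The design makes EUS-FNA the expected driver of change.** Patients enter because histology is needed for the treatment decision, and MTM2 is set according to the pathology result. The comparison covers only the nodes described at inclusion, so many staging findings or symptoms would not alter the entry. This narrows the problem but does not remove it.
- **Impact has a companion measure.** Clinical utility depends on the puncture result and the reference test, and gives no credit to a puncture that is undiagnostic or refuted. That stands, but it does not correct the strategy-change rate, which is reported separately.
- **The bias is not measured and need not always run upward.** If other information would have changed the plan and EUS-FNA restored it, the rule records no impact. The illustrative excess is also mostly within the sampling error at n = 50. Both points stand, although a systematic excess does not average out as sampling error does.
- **The document is a study summary.** The MTM forms are not shown, so a reason for change may already be collected. The finding is therefore that this document has no attribution step; even if reasons are collected, the stated rule does not use them.

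A reader might infer that other results do arrive between the meetings, or that up to six weeks separate them. The documents support neither: no section mentions intervening results, and the six-week limit runs from PET to endoscopy. A reader might also infer that an undiagnostic puncture followed by any change certainly counts as impact; that depends on which of the two population statements governs.

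**Conclusion.** The point holds in limited form. As written, the rule credits EUS-FNA with every change of strategy for the mediastinal nodes, whatever its cause, while the objective asks for the change relative to PET alone. This is a stated rule that can mislead, not just a missing detail.

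The size is unknown. The illustrated excess of 3 to 9 points at a true 40%, or 4 to 12 points at a true 20%, rests entirely on an assumed other-cause rate of 5% to 15%, on independence, and on other causes only adding discrepancies. It should not be quoted as an estimate of the bias in this trial.

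Severity is low. The endpoint is secondary and descriptive, the study is exploratory, and the primary sensitivity result is unaffected.

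**What to change.** - On the MTM2 form, record for each changed strategy whether the EUS-FNA result was the reason, and what new information has arisen since MTM1.
- Count as impact only the changes attributed to EUS-FNA. Report the crude MTM1/MTM2 change rate beside it, labelled as descriptive.
- Reconcile the all-patients statement in the Evaluation criteria with the contributory-only population in the Statistical analysis row, so that it is clear whether patients with an undiagnostic puncture are counted.

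Recording a strategy at MTM2 before disclosing the EUS-FNA result would be a cleaner contrast in principle, but it is less credible here because that meeting is convened on the pathology result.

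The cost is one extra line on the form. The attribution is an unblinded judgement of cause, which is why the crude rate should stay visible. Inclusions began in the second half of 2012 and this version dates from July 2016, so patients already past MTM2 would have only the crude measure; the report should state how many patients have each.

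### The planned precision for sensitivity, [89%; 100%] at 95% on 50 patients, is a truncated Wald interval whose lower limit is about 4 points too high, and no interval method is named for the analysis

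*Combined protocol and SAP*

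**What the plan says.** In the combined protocol and SAP, the row on the number of inclusions describes an exploratory pilot. No formal sample-size calculation was made. The 50 patients were chosen from what the centre could recruit and from an acceptable precision of the estimates. The only precision figure offered is "precision of the sensitivity and specificity estimate would be 12% for an expected sensitivity of 95% (95% confidence interval: [89%; 100"%. No formula is named. The same row says that the 95% is taken from a published study of EUS-FNA combined with PET, "but for histology data, whereas in our project we will have cytology data".

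The evaluation criteria define sensitivity "among all the subjects considered to be suffering from a neoplastic pathology according to the reference test". Its denominator is therefore 50 only if every patient has malignancy. The analysis set is further limited to patients with a contributory puncture.

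The statistical analysis row closes with "Qualitative variables will be described on the basis of the proportions and presented with their 95% confidence interval". Again no method is named.

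**The concern.** An interval for a proportion near 95% on 50 subjects should be clearly asymmetric, with its lower arm longer than its upper arm. The printed interval looks like a symmetric one that ran past 100% and was cut. There is a second sign: the stated 12% is wider than the printed interval, which spans only 11 points.

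Sensitivity is the primary endpoint. The trial tests no hypothesis, so the confidence interval is its main inferential output, and acceptable precision is one of the stated grounds for 50 patients. If the planning interval is too favourable, readers expect a tighter lower bound than the trial can give. If the same formula were used for the results, intervals would cover too rarely, and a proportion of 100% would get an interval of zero width.

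**Working it through.** **Inputs.** From the row on the number of inclusions: n = 50, expected sensitivity p = 0.95, two-sided 95% confidence (z = 1.96), stated result [89%; 100%] with precision 12%. The expected number of malignant patients is not in the documents; the values 40, 30 and 20 below are assumptions.

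**Step 1: reproduce the plan's figure.** The Wald interval is p ± z·√(p(1−p)/n).

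- 1.96 × √(0.95 × 0.05 / 50) = 1.96 × √0.00095 = 0.0604.
- Limits: 0.95 ± 0.0604 = 88.96% to 101.04%.
- Full width: 12.1 points.

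Cutting the upper limit at 100% gives the printed interval. The 12% is the full width before the cut. At n = 50, none of the other formulas tried matches: continuity-corrected Wald 88.0% to 102.0%, Wilson 85.1% to 98.4%, Clopper-Pearson 84.8% to 99.2% (continuous form, since 95% of 50 is 47.5), Agresti-Coull 84.5% to 99.1%, Jeffreys 86.3% to 98.7%.

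At p = 0.95 the Wald upper limit passes 100% whenever 1.96 × √(0.0475/n) > 0.05, that is for every n below 73.

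**Step 2: the same inputs with a method suited to p near 1.** Wilson: [p + z²/2n ± z·√(p(1−p)/n + z²/4n²)] / (1 + z²/n), with z² = 3.8416.

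- Centre: (0.95 + 0.0384) / 1.0768 = 0.9179.
- Half-width: 1.96 × √(0.00095 + 0.000384) / 1.0768 = 0.0665.
- Limits: 85.1% to 98.4%, width 13 points.

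The Wald lower limit is 88.96 − 85.14 = 3.8 points higher. With whole counts, Clopper-Pearson gives 83.5% to 98.7% for 47/50 and 86.3% to 99.5% for 48/50. The Wald lower limits for those counts are 87.4% and 90.6%, which are 4.0 and 4.3 points higher (from unrounded limits).

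**Step 3: coverage and gap by denominator.** Exact coverage at a true sensitivity of 95% is the sum of binomial probabilities over the counts whose interval contains 0.95.

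| Malignant patients | Wald lower limit | Wilson interval | Gap (points) | Wald coverage | Wilson coverage | P(all detected) = 0.95ⁿ |
|---|---|---|---|---|---|---|
| 50 | 89.0% | 85.1% to 98.4% | 3.8 | 92.0% | 96.2% | 7.7% |
| 40 (assumed) | 88.2% | 83.5% to 98.6% | 4.7 | 86.8% | 95.2% | 12.9% |
| 30 (assumed) | 87.2% | 80.9% to 98.8% | 6.3 | 78.2% | 93.9% | 21.5% |
| 20 (assumed) | 85.4% | 76.4% to 99.1% | 9.1 | 63.9% | 92.5% | 35.8% |

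Gaps are taken from unrounded limits. The Wald shortfall comes almost wholly from the outcome in which every malignant patient is detected. At n = 50 the interval misses with probability 8.0%, of which 7.7 points are that outcome.

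The 92.0% is specific to a true value of 95%. At n = 50, Wald coverage is 94.1% at a true 85%, 87.9% at 90%, 86.6% at 93% and 78.1% at 97%.

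**Step 4: what a result of 100% would look like.** With p = 1 the Wald half-width is 0, so the interval is [100%; 100%]. The exact lower limit for n out of n is 0.025^(1/n): 92.9% for 50/50 and 91.2% for 40/40. For an NPV of 10/10, a purely illustrative count, it is 69%.

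**The case against.** The strongest reply is that this is a planning illustration in an exploratory pilot. No success threshold is set on the lower limit, and the number of patients came largely from feasibility. At the plan's own values the width moves only from 12 to 13 points and coverage is 92.0% instead of 95%, a modest shortfall. The larger shortfalls need denominators of 40 or fewer, which the documents do not state. All of this stands, and it limits the severity. It does not make the printed interval right: precision is one of the stated grounds for 50 patients, and nothing elsewhere in the document corrects the figure.

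Five stronger readings are tempting, and the documents do not support them:

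- *That the plan will analyse its data with Wald intervals.* Wald is the only method seen in use, and even that is inferred from the numbers. The statistical analysis row leaves the method open, so the zero-width interval is a possibility to close off and not something the plan prescribes.
- *That the lower limit is 4 points too high at any denominator.* The 4 points belong to n of about 50. At 95% the gap to Wilson is 9.1 points at n = 20 and 1.9 at n = 100.
- *That NPV is expected near 100%.* The documents give no expected NPV.
- *That the sample size is invalid.* It was not derived from this interval alone, and correcting the interval changes no enrolment figure.
- *That wider intervals at a true 80% to 90% show the Wald error.* At n = 50 the Wald and Wilson widths there are almost equal: 16.6 and 17.0 points at 90%, 19.8 and 19.7 at 85%, 22.2 and 21.8 at 80%. Those widths bear on the choice of 95%, whose histology source the plan itself discloses.

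**Conclusion.** The point holds, at moderate weight. The plan's single precision statement for its primary endpoint reproduces as a Wald interval cut at 100%. Its lower limit is about 4 points too favourable even in the best case of 50 malignant patients, and the nominal 95% interval covers 92.0% of the time at a true 95%. Within the assumed range of 20 to 50 malignant patients, at a true 95%, both errors grow as the count falls. The true denominator is probably below 50, because it counts only reference-positive patients with a contributory puncture, but the documents do not allow it to be fixed. For the analysis, the defect is an unnamed method, not a wrong one. The identification of Wald rests on numerical agreement, since no formula is given.

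**What to change.** Two edits.

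1. In the row on the number of inclusions, replace the 12% and its interval with the Wilson interval: about 85% to 98%, width 13 points, for an expected sensitivity of 95% and 50 malignant patients. Say that the figure is the full width. Add the same interval for smaller malignant counts, labelled as assumptions, for example 83.5% to 98.6% for 40 and 80.9% to 98.8% for 30. Showing true sensitivities of 80% to 90% is optional and would address the histology source of the 95%.
2. In the statistical analysis row, state that sensitivity, NPV and all other proportions are reported with two-sided 95% Wilson intervals. Clopper-Pearson is an acceptable alternative; it is more conservative (98.8% coverage at n = 50 and a true 95%).

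The cost is a few sentences and a slightly less favourable stated precision. The number of patients, the procedures and the endpoints do not change. The method should be fixed before results are seen.
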